4. SAMPLE SIZE AND POWER

Approximately 100 patients diagnosed with RA will be recruited. The sample size was calculated by assuming an alpha of 0.05 and a power of 0.80 in a two-sided test, resulting in 52 subjects required to recognize a statistically significant improvement in HAQ DI (-0.21) (11). Given the importance of other secondary endpoints, an improvement of 9.9 ± 25 hours of work time lost requires 58 subjects, assuming an alpha of 0.05 and a power of 0.80 in a two-sided test (12). However, since it is expected that approximately half the study population may no longer be working due to their age, approximately twice this number (100 patients) will be required to achieve the required number of respondents. We have also assumed a drop-out rate of 13% (assuming between 10%-15%).

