Approximately 100 patients diagnosed with RA will be recruited. The planned sample size provides at least 95% power for detecting a statistically significant improvement in HAQ-DI (Δ HAQ-DI < 0) assuming a mean Δ HAQ-DI of -0.21 and a standard deviation of 0.5 (reference 11), at two-sided significance level of 0.05 and accounting for a 10% dropout rate. The sample size also provides at least 95% power for detecting a statistically significant clinically meaningful improvement in HAQ-DI (Δ HAQ-DI < -0.22) assuming a mean Δ HAQ-DI of -0.5 and a standard deviation of 0.7, at two-sided significance level of 0.05 and accounting for a 10% dropout rate. For the secondary endpoint WPAI, the sample size provides 63% power for detecting a statistically significant improvement in “hours of work lost” at two-sided significance level of 0.05 and accounting for a 10% dropout rate, assuming a mean change in “hours of work lost” of 10 and standard deviation of 30 and assuming a 55% employment rate in the study population.

9.6 **Data Management and Storage Process**

9.6.1 **Data Management**

Data management and data quality check will be performed to remove errors and inconsistencies in order to assure the appropriateness of the study data set to assess the study objectives. Data entry screens will be developed and tested prior to initiating data collection to reduce data entry errors. If required, IMS will provide AbbVie with data for analysis.

Each site coordinator will be instructed to answer patients’ queries which may arise in relation to the questionnaires and check the patients’ input to make sure all questions are answered.

9.6.2 **Storage Process**

Following data quality checks, each dataset will be converted to SAS and merged for analysis. All information included in the CRF and the patients’ questionnaires will be checked in order to detect possible queries to solve and will be extracted to a specifically designed database, where it will be validated by IMS personnel to ensure its quality. Finally, data analysis will be conducted and final results reported.

The databases will be stored in IMS data servers. Data servers are submitted to daily backups in order to increase the security on all data managed in the collection process.

All paper based questionnaires will be stored in a secured, locked area for a period of seven (7) years, after which all data will be shred using an agency specialized in disposal of confidential documents.

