9.7.5 Secondary Endpoint Analysis

The main secondary endpoint variable will be the change in HAQ DI at 12 weeks after the initiation of adalimumab.

The objective of endpoint analysis will be to demonstrate that treatment with adalimumab improves functioning as measured by HAQ DI in subjects with RA compared to baseline.

The main secondary analysis will be summarized as the mean and 95% confidence interval and will be tested with a paired t-test without adjusting for baseline disease severity. For sensitivity analysis, the mean change in HAQ DI at Week 12 will be analyzed using ANOVA adjusting for baseline disease severity.

Other secondary analyses include:

- Change in other patient reported outcomes (SF-36 domain scales, EQ-5D Index, WPAI total lost productivity) at weeks 12 and 24 after the initiation of adalimumab, in those patients continuing on adalimumab (as observed population). These changes will be summarized as the means and 95% confidence intervals and will be tested with paired t-tests.
- Number and percent of patients achieving a clinically meaningful improvement on the HAQ DI, as defined by a -0.22 point improvement or greater, at weeks 12 and 24 after the initiation of adalimumab, in those patients continuing on adalimumab (as observed population).

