5.4 Analysis Plan for Secondary Objectives

In addition to HAQ DI score, the effect of adalimumab will also be assessed by the secondary outcome measures which are changes to the Short Form 36-Item Health Survey (SF-36) domain scores, EuroQol 5 dimension 3 level (EQ-5D-3L) index, WPAI outcomes, and Patient Treatment Satisfaction Questions at 12 and 24 weeks after the initiation of adalimumab in RA.

- As to the Short Form 36-Item Health Survey (SF-36) domain scores, the Excel Table 4 summarizes the changes in PCS T-score and MCS T-score at 12 and 24 weeks after the initiation of adalimumab; these changes will be summarized as the mean, SD, minimum, maximum, median, 95% confidence interval; and the mean change will be tested with paired t-tests with p-value listed in the table.
- As to the EuroQol 5 dimension 3 level quality of life questionnaire, the Excel Table 5 summarizes the changes in EQ-5D-3L index at 12 and 24 weeks after the initiation of adalimumab; these changes will be summarized as the mean, SD, minimum, maximum, median, 95% confidence interval; and the mean change will be tested with paired t-tests with p-value listed in the table.
- As to the WPAI outcomes, the Excel Table 6 summarizes the changes in percent overall work impairment and percent activity impairment at 12 and 24 weeks after the initiation of adalimumab; these changes will be summarized as the mean,

SD, minimum, maximum, median, 95% confidence interval; and the mean change will be tested with paired t-tests with p-value listed in the table.

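### SAP Section 4 calls 100 patients about twice 58, but twice 58 is 116; on the SAP's own inputs 100 patients give 72–74% power for work time lost, not 80%, and the protocol states 63%

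*SAP*

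**What the plan says.** SAP Section 4 gives two sample sizes, both at two-sided 0.05 and 80% power. One is 52 subjects for a HAQ DI change of -0.21. The other is for a work-time change of 9.9 ± 25, where the stated amount of "hours of work time lost requires 58 subjects, assuming an alpha of 0.05 and a power of 0.80 in a two-sided test". The section then expects that "approximately half the study population may no longer be working due to their age" and concludes that "approximately twice this number (100 patients) will be required to achieve the required number of respondents". It closes with "We have also assumed a drop-out rate of 13" percent, giving a range of 10% to 15%.

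Protocol 9.5, repeated in the abstract, also plans about 100 patients. It states: "For the secondary endpoint WPAI, the sample size provides 63% power for detecting a statistically significant improvement in" hours of work lost. Its inputs are a mean change of 10, a "standard deviation of 30 and assuming a 55% employment rate in the study population", and 10% dropout.

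The tested variables have other names. Protocol 9.7.5 lists "Change in other patient reported outcomes (SF-36 domain scales, EQ-5D Index, WPAI total lost productivity) at weeks 12 and 24". SAP 5.4 plans paired t-tests on "changes in percent overall work impairment and percent activity impairment at 12 and 24 weeks".

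**The concern.** A requirement of 58 working subjects, with half of patients working, leads to 116 patients, not 100. The work endpoint is the SAP's only stated reason for going beyond 52 to 58 patients, so the error sits in the justification of the trial's size.

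The SAP and the protocol also describe the same 100 patients with different effects, SDs, employment rates, dropout rates and power. Someone reading only the SAP would judge a null work-productivity result against 80% power. A reader of the protocol would use 63%.

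Both figures concern hours of work lost. Under SAP 3.5.1, hours missed (Q2) enter percent overall work impairment only through Q2/(Q2+Q4). Percent activity impairment is Q6/10 and uses no hours. In protocol Appendix G, patients who are not employed skip to Q6 and still answer it, so the employment discount does not apply to that score.

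**Working it through.** **Inputs.** SAP Section 4: change 9.9, SD 25 (reading the ± as an SD), two-sided 0.05, 80% power, about 50% employed, 13% dropout (10–15%). Protocol 9.5: change 10, SD 30, 55% employed, 10% dropout; HAQ DI change -0.21, SD 0.5. Both documents: about 100 patients and a paired t-test on change.

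**Step 1. Reproduce the 58.** The normal-approximation formula is n = ((z₀.₉₇₅ + z₀.₈₀) × SD/δ)².
- Standardised effect: 9.9/25 = 0.396.
- n = (1.960 + 0.842)²/0.396² = 50.05 completers, using unrounded z values.
- With 13% dropout: 50.05/0.87 = 57.5, rounded up to 58.

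The HAQ DI figure follows the same pattern with the protocol's SD. The effect is 0.21/0.5 = 0.42, n = 44.49, and 44.49/0.87 = 51.1, rounded up to 52. Without any dropout the formula gives 51 (normal) or 53 (exact t) for work time, not 58. Some dropout allowance is therefore already inside the 58.

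**Step 2. From 58 to enrolment.**
- 58/0.50 = 116. The ratio 100/58 is 1.72.
- Check: 116 × 0.50 × 0.87 = 50.5 completers, which gives 80% power (normal).
- 100 appears only as 50.05/0.50 = 100.1, which leaves the dropout out.
- If 58 were read as completers, with dropout on top, the requirement would be 58/(0.50 × 0.87) = 133.3, so 134.

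**Step 3. Power with 100 patients on the SAP's inputs.** Normal power is Φ(0.396√n − 1.960). Exact power uses the noncentral t.

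| Dropout | Employed completers | Exact t | Normal |
|---|---|---|---|
| 10% | 100 × 0.50 × 0.90 = 45.0 | 74% | 76% |
| 13% | 100 × 0.50 × 0.87 = 43.5 | 72% | 74% |
| 15% | 100 × 0.50 × 0.85 = 42.5 | 71% | 73% |

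At 13%, for example, 0.396 × √43.5 = 2.612, and Φ(2.612 − 1.960) = Φ(0.652) = 0.743. For 100 patients to supply 50.05 completers, the employed share would have to be 50.05/87 = 57.5%.

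**Step 4. Reproduce the protocol's 63%.** 100 × 0.55 × 0.90 = 49.5 completers. With 10/30 = 0.333, power is 63.3% by exact t (65.0% normal), so the stated figure reproduces.

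**Step 5. Where the documents part.** With the protocol's 49.5 completers but the SAP's 9.9/25, power is 78% (t) or 80% (normal). Changing only the effect and SD to 10/30 brings it to 63% (t). Most of the conflict therefore comes from the effect and SD, not from employment or dropout.

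**Step 6. Primary endpoint.** HAQ DI at 0.42 with 87 to 90 completers has 97–98% power by either method.

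**The case against.** The strongest reply accepts the arithmetic and questions how much it matters.

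- *The dropout inside the 58 is inferred.* The SAP does not say it is there, and other routes give both numbers. Exact t with 10% dropout yields 52.0/0.90 = 57.8 and 46.45/0.90 = 51.6, which round up to 58 and 52. This stands: the 13% normal-method route is not unique. It changes neither the 116 nor the 71–76% range.
- *Every term is approximate.* With 55% employed, 58/0.55 is about 105, and with 10% dropout 100 patients come close to 80%. That is true, but 55% is the protocol's input. The SAP says about half and doubles on that basis. No reading that keeps 58, one half and the dropout gives 100.
- *The 63% rests on other inputs.* That is correct. It shows a conflict between documents, not an arithmetic error in the protocol. The protocol's amendment log records a sample size calculation change on 01/10/2015, so the SAP may carry older planning text. Both texts are nevertheless current.
- *The protocol's inputs are less well sourced.* The SAP cites a reference for 9.9 ± 25, whereas protocol 9.5 gives none for 10 ± 30. This stands, and the source should be stated.
- *It cannot affect conduct.* Planned database lock was 28 February 2017, and the SAP cites table shells dated January 2018. SAP 5.4 also reports a 95% confidence interval for each WPAI change. This limits the harm to interpretation and is a reason not to ask for more patients.

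**Conclusion.** The concern holds and should be fixed. SAP Section 4 is 16 patients short of its own doubling rule (116 against 100). Its inputs give 72–74% power at 13% dropout, or 71–76% over its stated dropout range, against the 80% it claims. The protocol's 63% for the same enrolment is correct on its own inputs and incompatible with the SAP. Neither figure describes the percent scores named in SAP 5.4.

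The conclusion assumes that ± 25 is an SD of change, that about half means 50%, and that the SAP's dropout applies to the 100 enrolled. The endpoint is secondary, and the primary HAQ DI analysis is unaffected.

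**What to change.** Replace SAP Section 4 with the protocol 9.5 statement and its inputs: at least 95% power for HAQ DI, and 63% for hours of work lost (10 ± 30, 55% employed, 10% dropout). Delete the 58-subject, 80% and doubling justification. State the source of 10 ± 30, or say that it is a planning assumption.

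Add one sentence: *The power figure for hours of work lost does not apply to percent overall work impairment or percent activity impairment, which are the WPAI scores tested.* Say in the same place which of these scores corresponds to the protocol's total lost productivity, a term that neither document defines.

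A descriptive row for change in WPAI Q2 hours is optional. It should not be presented as the powered variable unless the 10 ± 30 is confirmed to be on Q2's seven-day scale, which neither document states.

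The cost is SAP wording only, and the SAP's stated power for the work endpoint falls from 80% to 63%. Do not enrol more patients. Data collection and the planned tests stay as they are.

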5. STATISTICAL ANALYSIS

5.1 General Considerations

The statistical analysis will be performed using SAS® 9.3 software or a later version (SAS Institute, North Carolina, USA) via SAS Enterprise Guide version 6.1. The statistical results will be displayed using tables, listings and/or graphs. Figures will be performed with SAS®.

Unless otherwise specified, results will be provided as descriptive statistics. For categorical measures, data will include the frequency (number of cases [N]) and percentage (%) of total study patients observed in each category. Continuous variables will be described with number of patients with missing observations, mean, standard deviation (SD), median, minimum, and maximum.

The following rules will be followed to define the number of decimal positions to report in study results:

- For categorical variables:
 - 1 for the percentage.
- For most of the continuous variables:
 - 1 for the mean, SD, median, minimum, and maximum.
 - In continuous variables with low values, 2 decimals for all measures will be reported.

A set of draft table shells (see the document, "AbbVie_ROCKI_Tableshell_V0.2_2Jan2018_Taiwan.xlsx") will be created in advance to describe the statistical analysis that will be done to fulfill the objectives of this study. Based on the analysis results the tables will be modified accordingly.

5.2 Analysis Plan for Demographic and Clinical Characteristics

- Descriptive statistics will be presented for patient demographics (Excel Table 1), and clinical characteristics (Excel Table 2) for all patients. The following measures will be assessed as of the patient's baseline:
 - Patient age (mean, SD, minimum, maximum, median; categories: 18-34, 35-44, 45-54, 55-64, 65-74, 75+, missing)
 - Gender (male, female, missing)
 - Marital status (married, unmarried, missing)
 - Medical insurance type (National/Public insurance, Private insurance, Employer benefits, other, no insurance, missing)
 - Disease Activity Score in 28 joints - DAS28 (mean, SD, minimum, maximum, median; categories: Remission, Low Disease Activity, Moderate Disease Activity, High Disease Activity, Missing)
 - Number of patients with each of the comorbidities at baseline visit (See 3.5.2), and number of patients with any of these comorbidities

5.3 Analysis Plan for Primary Objectives

The objective of the primary endpoint analysis will be to demonstrate that treatment with adalimumab improves functioning as measured by the HAQ DI score in subjects with RA following treatment initiation (i.e. baseline).

- The changes in HAQ DI score at 12 and 24 weeks after the initiation of adalimumab will be presented (Excel Table 3.1); these changes will be summarized as the mean, SD, minimum, maximum, median, 95% confidence interval; as well as the number and percent of patients achieving a clinically meaningful improvement on the HAQ DI, as defined by a -0.22 point improvement or greater. In addition, the mean change will be tested with a paired t-test without adjusting for baseline disease severity, shown by p-value1; for sensitivity analysis, the mean change will be analyzed using ANOVA adjusting for baseline disease severity, shown by p-value2 in the table.
- The change in HAQ DI score at 24 weeks after the initiation of adalimumab (mean, SD, minimum, maximum, median, 95% confidence interval), in those patients continuing on adalimumab (observed population) will be compared with those patients not continuing on adalimumab (withdrawal population). The mean changes in these two groups will be compared using an independent t-test with p-value listed in the table (Excel Table 3.2).

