Subjects that initially screen fail for the study may be permitted to re-screen following re-consent. All screening procedures with the possible exceptions noted below will be repeated. The subject must meet all inclusion and none of the exclusion criteria at the time of re-screening in order to qualify for the study. There is no minimum period of time a subject must wait to re-screen for the study. If the subject had a complete record of eligible criteria including a PPD test (or equivalent), or Interferon-Gamma Release Assay (IGRA; QuantiFERON-TB Gold In-Tube test or T-SPOT TB test), Chest x-ray (if applicable) and ECG no more than 3 months (90 days) have passed, these data will not be required to be repeatedly collected for re-screening. As appropriate, sites are encouraged to contact the AbbVie Medical Monitor to confirm if subjects should or should not be re-screened.

9.2.1 Inclusion Criteria:

Patients meeting all of the following inclusion criteria at baseline will be included:

1. Subject has a diagnosis of RA as defined by the 1987 revised ACR classification criteria and/or the ACR/ the European League against Rheumatism (EULAR) 2010 classification criteria (any duration since diagnosis)
2. Male or female subjects ≥ 18 years of age (local definition according to adalimumab label) who is in compliance with eligibility for adalimumab based on the local label
3. Patients with moderate to severe RA defined as DAS28 (ESR) or DAS28 (CRP) > 3.2

4. Biologically treatment naïve and initiated adalimumab at baseline visit
5. Availability of clinical data of the previous 12 weeks prior to baseline
6. Ability to self-complete patient questionnaires
7. Subject must be able and willing to provide written informed consent and comply with the requirements of this study protocol

Additional Inclusion Criteria

8. Female subjects who are either not of childbearing potential, defined as postmenopausal for at least 1 year or surgically sterile (bilateral tubal ligation, bilateral oophorectomy and/or hysterectomy) or are of childbearing potential and are practicing an approved method of birth control throughout the study and for 150 days after the Week 24 dosing or the last dose of adalimumab.

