9.7.4 Primary Endpoint Analysis

The primary endpoint variable will be the change in HAQ DI score at 24 weeks after the initiation of adalimumab, in those patients continuing on adalimumab (as observed population).

The objective of the primary endpoint analysis will be to demonstrate that treatment with adalimumab improves functioning as measured by the HAQ DI in subjects with RA following treatment initiation. This change will be summarized as the mean and 95% confidence interval and will be tested with a paired t-test without adjusting for baseline disease severity. For sensitivity analysis, the mean change in HAQ DI at Week 24 will be analyzed using ANOVA adjusting for baseline disease severity.

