9.9 Limitations of the Research Methods

The study is to be performed as a non-interventional study. Unlike clinical studies, obtainable data are limited and there is a possibility of missing data.

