1. Arthroscopy 2. Carpal tunnel release 3. Cervical spinal fusion 4. Total knee replacement 5. Total hip replacement 6. Knee arthrodesis (fusion) 7. Hip arthrodesis (fusion) 8. Synovectomy 9. Other: _____			

* For day surgeries, please input 0 days.

6. Please check any Hylan G-F 20 (Synvisc) injections this patient has received for her/his Rheumatoid Arthritis since the last completed survey.			
 No injection performed			
 Yes →	Injection Place	Dosage	Number of shots
	 1 Hip	_____ ml	_____
	 2 Knee	_____ ml	_____

1023259 Real-World Impact of RA

			-			
Site number	Participant ID					

7. Please check any adalimumab (Humira) injection this patient has received for her/his Rheumatoid Arthritis since the last completed survey.						
 No, no injection performed		Dosage	Number of Times			
 Yes →			_____ mg	_____		
Administration stop date (if stopped)		____/____/____ (DD/MM/YYYY)				

1023259 Real World Impact of RA
[Site number] - [Participant ID]

8. Please record all of the medications this patient has received for her/his Rheumatoid Arthritis since the last completed survey			
Drug Name	Average number of pills per day	Dose strength	Times per month
Disease Modifying Antirheumatic Drug (DMARD)			
 ₁ Auranofin (Ridaura, Myochrysine)	_____	_____ mg	_____
 ₂ Azathioprine (Imuran)	_____	_____ mg	_____
 ₃ Cyclosporine (Sandimmune and Neoral)	_____	_____ mg	_____
 ₄ Hydroxychloroquine (Plaquenil)	_____	_____ mg	_____
 ₅ Leflunomide (Arava)	_____	_____ mg	_____
 ₆ Methotrexate (Rheumatrex, Folex)	_____	_____ mg	_____
 ₇ Minocycline (Minocin, Dynacin and Vectrin)	_____	_____ mg	_____
 ₈ Sulfasalazine (Azulfidine)	_____	_____ mg	_____
 ₉ Others	_____	_____ mg	_____
Anti-inflammatory Drug (NSAID)			
 ₁₀ Ibuprofen (Advil, Motrin, Nuprin)	_____	_____ mg	_____
 ₁₁ Naproxen (Naprosyn, Anaprox, Aleve)	_____	_____ mg	_____
 ₁₂ Celecoxib (Celebrex)	_____	_____ mg	_____
 ₁₃ Aspirin (ASA)	_____	_____ mg	_____
 ₁₄ Diclofenac (Voltaren)	_____	_____ mg	_____

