2.1 Primary Objectives

- To describe the change in HAQ DI score at 24 weeks after the initiation of adalimumab (i.e. baseline), in those patients continuing on adalimumab (as observed population). This change will be summarized as the mean and 95%

confidence interval and will be tested with a paired t-test without adjusting for baseline disease severity. For sensitivity analysis, the mean change in HAQ DI at Week 24 will be analyzed using ANOVA adjusting for baseline disease severity.

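### The primary analysis sets out to demonstrate that adalimumab improves functioning, but an uncontrolled paired t-test can only describe the change after starting it, and co-medication enters no HAQ DI analysis

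*SAP*

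**What the plan says.** The aim is worded in two ways.

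- SAP 2.1: "To describe the change in HAQ DI score at 24 weeks after the initiation of adalimumab (i.e. baseline), in those patients continuing on adalimumab".
- SAP 5.3: the primary analysis "will be to demonstrate that treatment with adalimumab improves functioning as measured by the HAQ DI score in subjects with RA following treatment initiation".
- Protocol 9.7.4: "The objective of the primary endpoint analysis will be to demonstrate that treatment with adalimumab improves functioning as measured by the HAQ DI". Protocol 9.7.5 repeats the aim for Week 12.

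The analysis is the same in all three: "the mean change will be tested with a paired t-test without adjusting for baseline disease severity, shown by p-value1" (SAP 5.3). An ANOVA adjusted for baseline disease severity serves as sensitivity analysis. The only between-group comparison sets patients who continue adalimumab against those who withdraw.

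All patients are biologic-naïve, have DAS28 above 3.2 and start adalimumab at baseline (SAP 3.2.1). Their treatment follows usual practice and is not set by the protocol (SAP 3.1).

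The clinician CRF (Protocol Appendix C) records DMARDs and steroids with pills per day, strength and frequency. Baseline item 7 covers the previous 6 months and baseline item 11 covers current drugs. Follow-up item 8 reads: "Please record all of the medications this patient has received for her/his Rheumatoid Arthritis since the last completed survey".

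On limitations, beyond noting that the study is non-interventional, Protocol 9.9 says only: "Unlike clinical studies, obtainable data are limited and there is a possibility of missing data".

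**The concern.** To *describe* a change and to *demonstrate* a drug effect are different claims, and this design supports only the first. The paired test asks whether the mean change differs from zero. It cannot say why.

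Two other explanations are open. First, patients enter because their disease activity is above a cut-off, and physicians tend to start a biologic when a patient is doing badly. Some return towards the patient's usual level is to be expected. Second, a DMARD or steroid may be added at baseline or during follow-up.

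The stake is practical. Protocol 7.0 and SAP 1.1 say the evidence is meant to support reimbursement and pricing in Taiwan. A significant p-value under the SAP 5.3 wording would be read by payers as an adalimumab effect of the observed size, and nothing in Protocol 9.9 would warn them otherwise.

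**Working it through.** **Inputs.** From Protocol 9.5: about 100 recruited, 10% dropout, two-sided 0.05, mean change -0.21 with SD 0.5, and a second scenario of -0.5 with SD 0.7 tested against -0.22. Assumed, because the documents give no value: a mean fall in HAQ DI of *b* = 0.05, 0.10 or 0.15 that is unrelated to adalimumab.

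**1. The plan's own power.**
- n = 100 × 0.90 = 90; critical t(0.975, 89) = 1.987.
- SD 0.5: SE = 0.5/√90 = 0.0527; noncentrality 0.21/0.0527 = 3.98; power 97.6% (noncentral t; normal approximation 97.9%).
- SD 0.7 against -0.22: SE = 0.7/√90 = 0.0738; noncentrality 0.28/0.0738 = 3.79; power 96.4%.

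Both agree with the stated figure of at least 95%. The sample size is sound for a before-after test.

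**2. Smallest mean change that reaches p < 0.05** = t(0.975, 89) × SE.
- SD 0.5: 1.987 × 0.0527 = 0.105, which is 0.105/0.22 = 48% of the plan's threshold for a meaningful improvement.
- SD 0.7: 1.987 × 0.0738 = 0.147, or 0.147/0.22 = 67%.

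**3. Chance of a significant result if the drug effect is zero and HAQ DI drifts by *b*** (noncentral t, df 89, noncentrality *b*/SE, two-sided).

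| Drift *b* | SD 0.5: *b*/SE | P(significant) | SD 0.7: *b*/SE | P(significant) |
|---|---|---|---|---|
| 0 | 0 | 5% | 0 | 5% |
| 0.05 | 0.95 | 16% | 0.68 | 10% |
| 0.10 | 1.90 | 47% | 1.36 | 27% |
| 0.15 | 2.85 | 80% | 2.03 | 52% |

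The power that makes the study efficient also makes it sensitive to a modest drift.

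**4. Where co-medication goes.**

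| Place | Use |
|---|---|
| Protocol 9.2.4.7 | Prior and current treatments are to serve for segmenting the population |
| Protocol 9.7.7 | Concomitant medications listed and summarised |
| SAP 5.5, Table 9 | Post-index number of patients with at least one medication, by category |
| SAP 5.3, Tables 3.1 and 3.2 (HAQ DI) | None |
| SAP 5.5, Table 11 (effect modifiers) | Not named; age, gender, baseline severity and comorbidities are |
| SAP 3.5.2 (clinical characteristics) | Not listed |

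So the data are reported, but no planned table shows a change in drugs from baseline, and none relates co-medication to HAQ DI.

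**5. Whether the planned extra analyses help.** Adjusting for baseline severity within a single treated cohort does not separate drug effect from drift. Patients who withdraw also started adalimumab, so they are not an untreated control.

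**The case against.** The strongest defence is that this is openly a non-interventional study. *Following treatment initiation* can be read as a statement about time, and SAP 2.1 already has the modest wording. Table 3.1 will also show the mean, its 95% confidence interval and the percentage reaching -0.22, so a small but significant change would be visible as small. That is fair and limits the harm. It does not remove the conflict between SAP 2.1 and 5.3, and a confidence interval does not reveal bias.

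The drift values have no source in the documents. They show sensitivity and do not estimate the bias. Entry is on DAS28, not HAQ DI, so the regression in HAQ DI depends on how far the two fluctuate together, which the documents do not say. At SD 0.7 the probabilities are clearly lower.

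Four stronger readings are tempting and not supported:

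- *The co-medication data go unused.* Table 9 and Protocol 9.7.7 summarise them. The gap is in the HAQ DI analyses.
- *Patients enter on high disease activity.* Entry is above 3.2, and both documents define high as above 5.1. A lower cut-off can still produce regression to the mean.
- *The protocol lets patients change DMARDs and steroids freely.* This is an inference from the non-interventional design. Protocol 9.2.6 and 9.8.2 mention prohibited medication, but no list is given.
- *Re-screening lets patients be retested until they qualify.* The protocol does say "There is no minimum period of time a subject must wait to re-screen for the study". But it also asks for re-consent and encourages sites to consult the Medical Monitor, and the ESR or CRP may be the latest value on record, so repeat scores need not be independent. Nothing in the documents turns this into a HAQ DI shift.

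**Conclusion.** The concern holds as a mismatch between the stated inference and the design. The planned mean change with its confidence interval is a valid description of patients who continue adalimumab. The claim that it demonstrates improvement by adalimumab is not supported, and the limitations section does not say so.

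At 90 patients, mean falls of 0.105 to 0.147 suffice for significance, below the plan's own 0.22. Assumed non-drug drifts of 0.05 to 0.15 would be declared significant 16% to 80% of the time at SD 0.5, or 10% to 52% at SD 0.7. The thresholds rest on the protocol's SDs and dropout; the probabilities rest also on the assumed drift.

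A reader might infer that adalimumab has no effect, or that most of any change would be artefact. The documents support neither; they give no means of dividing the change between drug and other causes.

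**What to change.** 1. **Wording.** In SAP 5.3 and Protocol 9.7.4 and 9.7.5, state the aim as describing the change in HAQ DI after starting adalimumab, in line with SAP 2.1. In Protocol 9.9, and alongside the results, state that there is no control group and that regression to the mean and co-treatment may contribute to the change.

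2. **One supplementary split in Table 3.1.** Report the Week 24 HAQ DI change (mean, 95% CI) by whether the recorded DMARD/steroid list stayed the same or had a drug added. Compare baseline item 11 with follow-up item 8, and item 7 with item 11 for drugs new at baseline. Protocol 9.2.4.7 foresees segmenting by treatment, and 9.7.3 allows up to two further subgroups. State the limits with the table:
   - Item 7 covers 6 months, so a drug started shortly before baseline appears in both lists and counts as not new.
   - Item 8 has no start dates.
   - Steroids are a single unnamed line, so dose increases across agents cannot be judged reliably.
   - The split informs about co-treatment. It does not remove confounding or regression to the mean.

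**Cost.** A few sentences and a few table rows, using data already on the CRF. The test, the sample size and data collection are untouched. The headline claim becomes weaker. No change to the re-screening rule is proposed.
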